Note that the medication from the suppository may stain fabric. Subjects may experience irritation such as burning, itching, dryness, skin/hair follicle irritation, or changes in skin color around the rectal area. Subjects are to report to the study staff any reactions that make continued application of the study medication difficult. The PI may recommend that the study medication be used less frequently on the irritated areas until the irritation goes away. If subject sees a doctor for any medical problems, they are to be advised to inform the study staff at their next visit. Subject is to record any illness or unwell feelings such as headaches, cold, cramps, etc., on the last page of their diary. Subjects are to record any change in medications since the previous visit (other than study medication) on the last page of the diary. All unused study medication must be returned to the study site at the end of treatment.

15. LABORATORY STUDIES:

comprehensive blood count (CBC), metabolic panel (CMP), blood HIV/Hepatitis B/Hepatitis C testing, urinalysis, urine pregnancy, urine drug screen, breath alcohol tests.

Protocol: HDCS 1701 Page 11 of 67 26Apr2019

16. DIAGNOSTIC TESTS:

Anoscopy - Classification of Internal Hemorrhoids (Banov et al. 1985).

Video of the procedure will be recorded and sent to the CRO for central reading.

Grade	Description
1	Hemorrhoids are visualized on anoscopy and may bulge into the lumen but do not prolapse below the dentate line
II	Hemorrhoids prolapse out of the anal canal with defecation or with straining but reduce spontaneously
III	Hemorrhoids prolapse out of the anal canal with defecation or straining, and require manual reduction
IV	Hemorrhoids are irreducible and may strangulate

17. RETENTION SAMPLES:

Retention samples will be randomly selected at the study sites from the clinical drug supplies received prior to dispensing to subjects and sent to BRR for long-term storage. Retention samples will not be returned to the sponsor at any time.

18. ADMINISTRATIVE MATTERS:

In addition to recording the time and date of each medication application, the Daily Personal Diaries will be used to record concomitant medication taken and all adverse events experienced. Paper copies of the IHSSA daily electronic diaries will be provided to subjects for use as a backup for missed ePRO questionnaires.

19. STUDY DISCONTINUATION:

Subjects could be discontinued from the study for the following reasons:

- a. Pregnancy.

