- b. The modified intent-to-treat (mITT) population includes all subjects who meet all inclusion/exclusion criteria, apply at least one (1) dose and return for at least one (1) post-baseline evaluation visit.
- c. The safety population (intent-to-treat (ITT)) includes all subjects who meet all inclusion/exclusion criteria and apply at least one (1) dose.

21. ENDPOINTS:

a. Clinician Reported Outcome (ClinRO) - Anoscopy (Visits 2, 4).

Anoscopy – Visual assessment of hemorrhoids (Fukuda et al. 2005; Lunniss and Mann 2004). Video of the procedure will be recorded for blinded central reading and assessment according to the following scale:

Swelling	% Lumen	Score	
	0	None	0
	≤25	Mild 1	
	≤50	Moderate 2	
	≤75	Severe	3
	>75	Very severe	4

b. Patient Reported Outcome (PRO) – Internal Hemorrhoid Sign and Symptom Assessment (IHSSA) (Daily between Visits 1 and 5).

Corporate Information

Corporate Information

post-bowel movement assessment, and end of day assessment are included in **Appendix 1**.

c. Patient Reported Outcome (PRO) – Patient Reported Outcome Measurement Information System (PROMIS) Global Health Questionnaire Version 1.2 (Visits 2 and 4).

The PROMIS Global Health Questionnaire is completed by patients during Visits 2 and 4. It will be completed before any clinical or laboratory tests are administered. The PROMIS Global Health Questionnaire assesses an individual's physical, mental, and social health using 10 items. The measure is generic, rather than disease-specific, and often uses an "In General" item context as it is intended to globally reflect individuals' assessment of their health. The questionnaire produces two scores: Physical Health and Mental Health. Raw scores for both scales are converted to T-scores with a mean of 50 and standard deviation of 10. The items of the PROMIS Global Health Questionnaire are included in **Appendix 2**.

d. Patient Reported Outcome (PRO) – Patient Global Impression of Severity (Visits 2 and 4) and Patient Global Impression of Change (Visit 4) Items

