The Patient Global Impression of Severity (PGIS) and Patient Global Impression of Change (PGIC) items are designed to capture the patient's overall perspective on sign and symptom severity. The 8-item PGIS asks patients to rate the severity of their hemorrhoid-related signs and symptoms over the past week. The 9-item PGIC asks patients to rate the direction and magnitude of the change in their signs and symptoms since starting the study medication. The PGIS and PGIC are included in the study to help establish the threshold for clinically relevant change on the IHSSA. Although they address signs and symptoms of internal hemorrhoids, the IHSSA is considered the primary measure of these constructs. The PGIS and PGIC items are included in **Appendix 3**.

Based on the results of the pilot study, primary and secondary endpoints will be selected for future studies.

22. SUBJECT SAFETY:

a. Safety assessment will be conducted on all subjects administered at least one suppository. Adverse drug reactions may include burning and local irritation upon application. Systemic absorption of topical corticosteroids has produced reversible suppression of the HPA axis. Adverse medical events experienced by the subjects will be tabulated. The relationship of adverse events, if any, to the study drug will be assessed by the Investigator (see Section 24).

26Apr2019 Protocol: **HDCS 1701** Page 14 of 67

b. Physical Examination

The investigator, sub-investigator or appropriately delegated designee, (Physician's Assistant, Advanced Registered Nurse Practitioner, and Registered Nurse as per local regulations) will perform a brief physical examination, prior to the Subject starting study drug.

The physical examination will include, at a minimum, examination of the Subject's general appearance, skin, HEENT (head, eyes, ears, nose and throat), heart, lungs, musculoskeletal system, neurological system, lymph nodes, abdomen and extremities.

Vital signs, including blood pressure, pulse rate, respiratory rate and oral body temperature will be documented at Visit 1. Vital signs will be measured after the Subject has rested in a seated position for at least 5 minutes.

The Subject's body weight will also be measured while the Subject is lightly clothed (e.g., no coat or shoes). Height will be measured without shoes.

c. Concomitant medications

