- ix. Obtaining additional tests to evaluate liver function, as appropriate (e.g., INR, direct
- Considering gastroenterology or hepatology consultations. X.

f. Pilot study stopping criteria

The pilot study may be stopped if ≥2 patients on drug develop the same CTCAE v4.0 Grade 3 adverse event or if 1 patient develops a CTCAE v4.0 Grade 4 or higher adverse event (Appendix 4).

23. STATISTICAL METHODS:

Endpoints

Anoscopy results at Day 15 will be compared to responses at baseline (Day 1). IHSSA scores from Days 1-15 (treatment period) and 16-29 (follow-up period) will be compared to responses from Days -14 to -1 (baseline period). The 95% confidence intervals for the differences between the change from baseline for the hydrocortisone acetate suppository and that for the placebo will be calculated.

b. Safety

The incidence of all AEs reported during the study will be classified based on Medical Dictionary for Regulatory Activities (MedDRA) version 21.0 terminology (system organ classes and preferred terms) and summarized for each treatment group. Incidence of adverse events will be tabulated by system organ class, preferred term, and severity, and by system organ class, preferred term, and relationship to study drug.

24. ADVERSE EVENTS:

Definitions

- Any untoward events occurring during the study will be documented and summarized upon completion of the study.
- The term Adverse Event (AE) will cover any untoward medical occurrence in a clinical investigation where a volunteer was administered an investigational product, which does not necessarily have to have causal relationship with this treatment. An adverse event can therefore be any unfavorable and unintended sign (including clinically significant abnormal laboratory finding, for example), symptom, or disease temporally associated with use of a medicinal product, whether considered related to the medicinal product. This includes all events both expected and unexpected (the nature or severity of which is not consistent with information in the relevant source document(s)).

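### Section 23 names no model or covariate: an unadjusted change-score comparison would be valid, but generally less precise than ANCOVA on baselines already collected

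*Combined protocol and SAP*

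**What the plan says.** The efficacy analysis in Section 23 is three sentences. Two fix the periods: "Anoscopy results at Day 15 will be compared to responses at baseline (Day 1") for anoscopy, and "IHSSA scores from Days 1-15 (treatment period) and 16-29 (follow-up period) will be compared to responses from Days -14 to -1 (baseline period") for the patient diary. The third says that 95% "confidence intervals for the differences between the change from baseline for the hydrocortisone acetate suppository and that for the placebo" will be calculated. No estimator, regression model, covariate, stratification factor or test is named there or elsewhere in the visible text.

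The trial randomizes about 100 subjects 1:1 (Sections 5 and 8). No power, effect size, SD or correlation is given. Section 21 states the purpose of the results: "Based on the results of the pilot study, primary and secondary endpoints will be selected for future studies".

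**The concern.** A plain difference in mean change subtracts the whole of each subject's baseline, which amounts to assuming that the regression slope of the post-baseline score on baseline is 1. If the true slope is lower or higher, the estimate carries an error of (slope − 1) times the chance difference between the arms in baseline mean. Over repeated randomizations that error averages to zero, so there is no bias. It does widen the interval. ANCOVA estimates the slope and removes this term.

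The confidence interval is the only between-arm efficacy inference that Section 23 specifies, and the pilot's results are to guide the choice of endpoints for later studies. Precision is therefore the main thing the choice of estimator can improve. Section 23 already uses the baselines that are needed. Silence also leaves the choice between adjusted and unadjusted results open, score by score, until after the data have been seen.

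**Working it through.** **Inputs from the protocol.** 50 per arm (Sections 5 and 8). Baselines are diary Days −14 to −1 and Day 1 anoscopy (Section 23). Entry requires an average of at least 1.5 on the 0–4 scale for either itch severity or itch frequency (Section 12, criterion a). Swelling is centrally read on a five-level score, 0 to 4 (Section 21.a: "Video of the procedure will be recorded for blinded central reading and assessment according to the following scale"). The plan derives no sample size or precision, so it has no figure of its own to reproduce.

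**Assumed, because the documents give neither.** Baseline to post-baseline correlation ρ from 0.3 to 0.9, and k = post-baseline SD / baseline SD at 0.75, 1 and 1.25. These are illustrations, not bounds.

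**Formulas** (baseline SD set to 1, n per arm, slope = ρk):

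- Unadjusted change: variance = (2/n)(1 + k² − 2ρk)
- ANCOVA, large sample: variance = (2/n) k²(1 − ρ²)
- Difference: (2/n)(1 − ρk)² = (slope − 1)² × (2/n), which is never negative

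With n = 50, 2/n = 0.04, so the SE of the baseline difference is √0.04 = 0.20 baseline SD.

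**Check at selected values:**

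| k | ρ | Slope | Unadjusted | ANCOVA | Avoidable |
|---|---|---|---|---|---|
| 1 | 0.5 | 0.5 | 0.0400 | 0.0300 | 0.25 × 0.04 = 0.0100 |
| 0.75 | 0.5 | 0.375 | 0.0325 | 0.0169 | 0.391 × 0.04 = 0.0156 |
| 1.25 | 0.5 | 0.625 | 0.0525 | 0.0469 | 0.141 × 0.04 = 0.0056 |
| 1.25 | 0.8 | 1 | – | – | 0 |

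**Small-sample cost of ANCOVA.** Its variance is multiplied by 1 + 1/96, and t has 97 rather than 98 degrees of freedom. Together these widen the interval by a factor of about 1.0053. For k = 1 and ρ = 0.5, √(0.0300/0.0400) × 1.0053 = 0.871, or 12.9% narrower. The half-widths are 0.397 SD unadjusted and 0.346 SD with ANCOVA.

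**Narrowing of the 95% interval with ANCOVA, 50 per arm (%; a negative value means wider):**

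| Scenario | ρ = 0.3 | 0.5 | 0.7 | 0.8 | 0.9 |
|---|---|---|---|---|---|
| k = 1 | 18.9 | 12.9 | 7.3 | 4.6 | 2.0 |
| k = 0.75 | 31.8 | 27.6 | 24.8 | 24.9 | 28.7 |
| k = 1.25 | 11.0 | 5.0 | 0.4 | −0.5 | 2.0 |
| Itch item strictly cut at 1.5 | 9.4 | 5.9 | 3.1 | 1.8 | 0.6 |
| Five-category swelling score | 19.9 | 14.2 | 8.9 | 6.4 | 3.8 |
| Same, no baseline score of 0 | 16.2 | 11.4 | 6.9 | 4.8 | 2.8 |

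The first three rows are closed form, and simulation (20,000 trials per setting) reproduces them within 0.1 point. The last three are simulated.

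- *Itch row.* Baseline is normal with mean 1.8 and SD 0.8, restricted to 1.5–4; ρ is the correlation before restriction. Hand check at ρ = 0.3: the restricted baseline SD is 0.522 (variance 0.273). The ANCOVA residual variance is 0.64 × 0.91 = 0.582, and the unadjusted variance is 0.582 + 0.49 × 0.273 = 0.716. Then √(0.582/0.716) × 1.0053 = 0.907, about 9.3% narrower.
- *Swelling rows.* A normal variable is cut at −1.5, −0.5, 0.5 and 1.5. Here ρ is on the underlying scale, so these rows are not strictly comparable with the others. The last row allows for entry requiring visible disease; Section 16 describes even the lowest grade with "Hemorrhoids are visualized on anoscopy and may bulge into the lumen".

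Coverage was 94.8–95.3% for both methods across all simulated settings.

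**Equivalent sample size, k = 1.** To match ANCOVA with 50 per arm, the unadjusted analysis needs 50 × 2/(1 + ρ), which is about 77, 67, 59, 56 and 53 per arm at the five correlations.

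**The case against.** The strongest reply is that the plan does not exclude ANCOVA. A baseline-adjusted difference in change also fits the sentence in Section 23, so under-specification is certain but a decision not to adjust is not. That stands: every loss figure is conditional on the unadjusted reading.

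Second, this is a pilot with no stated power, primary endpoint or rule based on interval width, and the intervals are valid either way. That also stands, and no claim is made that any particular endpoint choice would change.

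Third, the largest gains are the least supported. The entry rules on itch and bleeding narrow the baseline spread, which taken alone raises k. Symptom scores falling toward zero on treatment could offset this, but the documents give no figure. The k = 0.75 row therefore has no documentary support, and the restricted-itch and k = 1.25 rows show modest gains. The bleeding restriction was not modelled.

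Fourth, the diary is daily and has two post-baseline periods. A covariate does not settle how daily entries become one score or how missing days are handled. True, but both questions arise equally for the unadjusted analysis. Diary detail in Section 21.b and Appendix 1 is redacted, so nothing is held against the plan there.

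None of this removes the asymmetry: at worst ANCOVA costs about 0.5% in width, and away from a slope of 1 it narrows the interval.

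**Conclusion.** The point holds. Section 23 leaves the estimator unnamed. The unadjusted change-score comparison it most naturally describes is unbiased with correct coverage, but in large samples it is never more precise than ANCOVA and generally less so. With 50 per arm and equal SDs, ANCOVA narrows the interval by 19% to 2% as the correlation rises from 0.3 to 0.9. With an itch item strictly restricted at 1.5 the range is 9% to under 1%.

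The size rests on assumed SDs and correlations and on the inferred unadjusted reading, so confidence in it is moderate. This is a change worth making because it is nearly free. It corrects no bias and no invalid interval.

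**What to change.** Add to Section 23:

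> For each IHSSA score analysed as a continuous change from baseline, and for the anoscopy swelling score, the treatment difference and 95% CI will come from a linear model (ANCOVA) with treatment and the corresponding baseline score (IHSSA Days −14 to −1; Day 1 anoscopy) as covariate. The unadjusted difference will also be reported as a supportive result.

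The same model can serve other scores with a baseline if they are compared between arms as change. Section 21.d lists "Patient Global Impression of Severity (Visits 2 and 4) and Patient Global Impression of Change (Visit 4) Items", and Section 21.c says "The PROMIS Global Health Questionnaire is completed by patients during Visits 2 and 4". PGIC has no baseline, so the model does not apply to it. If adjustment is already intended, the sentence simply records it.

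The cost is one or two sentences and one degree of freedom, with an interval about 0.5% wider at 50 per arm if the slope is exactly 1. No new data, visits or patients are needed.

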Early hemorrhoids are frequently treated with a fiber diet and with lifestyle modifications such as increased exercise and the avoidance of obesity and sedentary occupation which appear to be significant risk factors for the disease. Also, control of diarrhea appears to be a useful option in the prevention of the development of hemorrhoids. However, in more advanced cases acute hemorrhoidal attacks are present with bleeding, inflammation and often thrombosis of the hemorrhoidal veins. Conservative therapy consists of local treatment. Several types of drugs have been used for this purpose. These include local anesthetics, chiefly pramoxine. This is a rapidly acting, local anesthetic which is applied topically as needed up to five times a day. It provides local relief particularly of itching through its anesthetic action. Local application of phenylephrine is also used in the treatment of hemorrhoids to reduce blood flow through the hemorrhoids by utilizing the drug's vasoconstricting action. This produces temporary relief of burning and itching. 5-amino salicylic acid (Mesalamine) is also used off-label as a local antiinflammatory agent to treat hemorrhoids. It appears to reduce the pain and bleeding of hemorrhoids during acute attacks. Hydrocortisone in various types of vehicles is also a prominent modality of treatment for hemorrhoids as well as other anorectal conditions. Foams, suppositories and locally applied creams have been used as vehicles for the application of hydrocortisone, although none are FDA-approved products for the treatment of hemorrhoids. Hydrocortisone's potent anti-inflammatory action is thought to reduce the inflammation associated with the hemorrhoids and thus improve bleeding, itching and other symptoms of hemorrhoids. Products using these ingredients have a long history of use in the United States and are commonly relied upon for the non-surgical, conservative treatment of hemorrhoids.

26Apr2019 Protocol: **HDCS 1701** Page 6 of 67 Version 4.0

3. OBJECTIVE:

- a. To determine the effectiveness of Nivagen's Hydrocortisone Acetate Suppositories 25 mg for the relief of symptoms associated with internal hemorrhoids.
- b. To determine the safety and tolerability of Nivagen's Hydrocortisone Acetate Suppositories 25 mg.
- 4. PHASE: 2

5. STUDY DESIGN:

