This study will be a randomized, double-blind, placebo-controlled, multicenter, parallel group pilot study of 25 mg hydrocortisone suppositories administered twice daily compared to a vehicle placebo in subjects with symptomatic internal hemorrhoids. Approximately 100 subjects will be randomized in a 1:1 ratio (Test product: placebo).

The study will consist of 3 periods:

- a. Screening Period (2 weeks/Days -14 to -1)
- b. Treatment Period (2 weeks/ Days 1-14)
- c. Follow-up Period (2 weeks/ Days 15-29)

Subjects will use daily paper diaries to record the time and date of each medication application, concomitant medication and adverse events (AEs). The subjects will use electronic diaries to complete the Internal Hemorrhoids Sign and Symptom Assessment (IHSSA) daily for the duration of the study and the Patient Global Impression of Severity (PGIS) and Change (PGIC) at visits.

6. STUDY POPULATION:

Male and female subjects, at least 18 years of age, with a diagnosis of symptomatic internal hemorrhoids will be selected to participate in the study.

7. PRODUCT DESCRIPTION:

Test Product: Hydrocortisone Acetate Suppository, 25 mg (Nivagen Pharmaceuticals Inc.) Placebo: Vehicle Suppository (Nivagen Pharmaceuticals Inc.)

8. GROUPS:

Two Groups (1:1) Total Subjects: Approximately 100 (50:50)

9. STUDY SCHEDULE:

Visit 1 (Days -14±2; Initiation of Screening)

Visit 2 (Day 1; Start of Treatment)

Visit 3 (Day 8±1, Interim)

Visit 4 (Day 15±2, End of Treatment)

Visit 5 (Day 29±3, Follow-Up/End of Study; UV/ED)

26Apr2019 Protocol: **HDCS 1701** Page 7 of 67 Version 4.0

10. STUDY OUTLINE:

Visit Title	Initiation of Screening	Start of Treatment	Interim	End of Treatment	Follow-up/End of Study UV/ED ⁸
Visit Number	Visit 1	Visit 2	Visit 3	Visit 4	Visit 5
Study Day	Day -14±2	Day 1	Day 8±1	Day 15±2	Day 29±3
Informed Consent	X				,
Medical History	X				
Demographics	X				
Concomitant Medication	37	37	37	37	37
Review	X	X	X	X	X
Physical Exam including Vital Signs	X				
Clinical Laboratory Tests	X ¹		X^2	X^3	
Urine Pregnancy Test ⁴	X	X	X	X	X
Urine Drug Screen	X				
Breath Alcohol Test	X				
Inclusion/Exclusion Criteria	X	X			
Adverse Events Assessment		X	X	X	X
Anoscopy		X		X	
Assessment of Disease Grade/ Diagnosis		X			
Randomization		X			
Cognitive Interview ⁵	X				
Exit Interview ⁶				X	
PROMIS Global Health		37			
Questionnaire		X		X	
IHSSA daily diary ⁷ (ePRO)	X	X	X	X	X
Patient Global Impression of Severity (PGIS) (ePRO)		X		X	

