- c. Surgical procedures themselves are not adverse events. They are therapeutic measures for conditions that required surgery. The condition for which the surgery is required is an adverse event, if it occurs or is detected during the study period. Planned surgical measures permitted by the clinical study protocol and the conditions(s) leading to these measures are not adverse events, if the condition(s) was (were) known before the start of study treatment. In the latter case, the condition should be reported as medical history.
- d. A serious adverse event is one that occurs at any dose (including overdose) and that:
- i. Results in death.
- ii. Is life-threatening.
- iii. Requires in-patient hospitalization or prolongation of existing hospitalization.
- iv. Results in persistent or significant disability or incapacity (defined as a substantial disruption of a person's ability to conduct normal life functions).
- v. Is a congenital anomaly or birth defect.
- vi. Is an important medical event (including development of drug dependence or drug abuse) that may jeopardize the volunteer or may require intervention to prevent one or the other outcomes listed above (according to medical judgment of the qualified investigator).
- e. Classification of Adverse Events
 - All adverse events will be recorded on an adverse event information sheet and graded as mild, moderate, or severe according to the following definitions:
- i. Mild: Causing no limitation of usual activities; the volunteer may experience slight discomfort.
- ii. Moderate: Causing some limitation of usual activities; the volunteer may experience annoying discomfort.

26Apr2019 Protocol: **HDCS 1701** Page 17 of 67 Version 4.0

- iii. Severe: Causing inability to carry out usual activities; the volunteer may experience intolerable discomfort or pain.
- f. Relationship to Study Medication

The relationship is characterized as:

- i. Not Related: This applies to any AE that is clearly not related to use of the study drug.
- ii. Possible: This means the association of the AE with the study drug is unknown; however, a relationship between drug and event cannot be ruled out.
- iii. Probable: There is a reasonable temporal relationship between the use of the study drug and the AE. Based upon the Principal Investigator's clinical experience, the association of the event with the study drug seems likely.

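### The local reactions named in advance are never counted together: Section 23.b plans only SOC/PT tables, with no grouped row, between-arm difference or interval

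*Combined protocol and SAP*

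**What the plan says.** Section 3.b sets the second objective: "To determine the safety and tolerability of Nivagen's Hydrocortisone Acetate Suppositories 25 mg".

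The expected local reactions appear in two places. Section 14 warns: "Subjects may experience irritation such as burning, itching, dryness, skin/hair follicle irritation, or changes in skin color around the rectal area". Section 22.a adds: "Adverse drug reactions may include burning and local irritation upon application".

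The adverse event analysis is confined to Section 23.b. Events are coded to MedDRA 21.0 "terminology (system organ classes and preferred terms) and summarized for each treatment group". Then: "Incidence of adverse events will be tabulated by system organ class, preferred term, and severity, and by system organ class, preferred term, and relationship". Severity has three levels, events being "graded as mild, moderate, or severe according to the following definitions" (Section 24.e), and relationship has four (Section 24.f). No section groups the named reactions, and none gives a between-arm difference or interval for adverse events.

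For efficacy the same section does plan estimation: "The 95% confidence intervals for the differences between the change from baseline" on drug and on placebo.

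The item on worsening under Definitions in Section 24 also matters. It says that worsening of the treated condition is normally captured through efficacy measures and need not become an adverse event unless it is serious.

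**The concern.** Burning, itching, dryness, follicle irritation and skin colour change would be reported in different words and would plausibly be coded to different preferred terms. With about 50 subjects per arm, one pattern of local intolerance could then be spread over several sparse rows, each split again by severity or relationship. A SOC row would pool some of the terms, but it would also take in unrelated events.

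What is at stake is the tolerability objective. The trial would have no single figure for how many subjects had a local reaction on drug and on vehicle, and no statement of uncertainty about the difference. That figure would be useful for planning the later studies to which Section 21 refers.

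**Working it through.** **Inputs from the protocol.** About 100 subjects, 1:1, so n = 50 per arm (Sections 5 and 8). Five reactions are named in Section 14. The protocol gives no adverse event rate and no power figure, so there is nothing of its own to reproduce.

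**Assumptions.** Five terms, equally frequent, one term per subject. The rates are illustrative.

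**Method.** For counts a and b out of 50, the Newcombe 95% interval combines the Wilson limits (l, u) of the two arms:

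- lower = d − √[(p1 − l1)² + (u2 − p2)²]
- upper = d + √[(u1 − p1)² + (p2 − l2)²], with d = p1 − p2.

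The chance that it excludes zero is the sum over all (a, b) of Bin(a; 50, π1) × Bin(b; 50, π2), taken where the interval excludes zero. Two-sided Fisher tests at 0.05 are given in brackets as a cross-check.

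**Step 1: what one sparse row can show.** For 3/50 vs 0/50 the Wilson limits are 0.021 to 0.162 and 0 to 0.071.

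- Lower = 0.06 − √(0.039² + 0.071²) = −0.02.
- Upper = 0.06 + 0.102 = 0.16.

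The difference is 6 points, interval −2 to 16, Fisher p = 0.24. No row with 0 to 3 subjects per arm has a smaller Fisher p-value. With none on placebo, 5 on drug gives p = 0.056 and 6 gives p = 0.027.

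**Step 2: one row against a combined row, 25% vs 5%.** Each row has 25%/5 = 5% vs 5%/5 = 1%, or 2.5 vs 0.5 subjects expected. The combined row expects 12.5 vs 2.5.

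- Given single row: interval excludes zero 6.6% of the time (Fisher 2.4%).
- At least one of five rows: about 30% by simulation (Fisher about 11%). Treating rows as independent gives 1 − (1 − 0.066)⁵ = 29%, in agreement.
- Combined row: 82% (Fisher 75%).

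At 20% vs 5%, a given row reaches 3.1% (0.9%) and the combined row 61.5% (51%).

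**Step 3: higher vehicle rates, combined row.**

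| Drug vs vehicle | Interval excludes zero | Fisher |
|---|---|---|
| 25% vs 15% | 24% | 17% |
| 20% vs 10% | 27% | 19% |
| 15% vs 10% | 10% | 6% |

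**Step 4: uneven spread.** If half of the reactions fall in one term, at 25% vs 5%, at least one row separates about 46% of the time (Fisher 31%), still below 82% (75%).

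**Step 5: SOC rows.** Suppose one SOC row collects 50 to 80% of the reactions. Its Fisher power is 45 to 78% at a pooled 30% vs 5% (grouped row 90%), and 19 to 44% at a pooled 20% vs 4% (grouped row 59%). Unrelated events in that SOC would dilute these figures.

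**Step 6: what a grouped row would report.** An observed 10/50 vs 2/50 gives a difference of 16 points, interval 3 to 29.

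**The case against.** The strongest objections concern how far the point can be pushed, and most of them stand.

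- *SOC rows already pool.* True. A reader might infer that reactions are tabulated only term by term, but SOC is a stated level of tabulation. Whether the named reactions share one SOC depends on the coding dictionary, which the documents do not show.
- *Sparse rows are an assumption.* True. A reader might infer that every row will hold 0 to 3 subjects and that a real excess would be read as no difference. In the 25% vs 5% scenario, all five active-arm rows hold 0 to 3 only about 23% of the time, and at least four of five rows favour placebo about 77% of the time. A count of 3 or fewer has probability 86% at a 4% term rate, but 25% at a 10% rate.
- *The comparator is the vehicle, inserted in the same way.* Irritation from vehicle or insertion would occur in both arms, so a fivefold excess is not supported by the documents. Step 3 shows how weak the combined row becomes.
- *One term per subject flatters pooling.* True. A subject with both burning and itching adds to two single rows but only once to the combined row.
- *Itching and burning are also disease symptoms.* Itch is an entry criterion on the daily IHSSA (Section 12.a), and Appendix 3 rates itching and burning on the PGIS. Under Section 24, worsening may never be recorded as an adverse event.
- *This is a descriptive pilot, and the subjects can be counted later.* No adverse event test is planned, so low power per row is not a failure of the plan. However, the remedy is an estimate, not a test, and a grouping chosen after unblinding is open to selection.

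Nor do the documents say that local reactions are the main tolerability question. Section 22 also raises HPA-axis suppression and liver injury.

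**Conclusion.** The point holds as a reporting gap. Tolerability is an objective, the local reactions are named in advance, and interval estimation is already used for efficacy. Yet no count of subjects with any local reaction, and no between-arm estimate, is specified.

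The benefit of closing the gap depends on unknown rates. Under the stated assumptions, the chance of an interval excluding zero at 25% vs 5% rises from about 30% (any of five rows) to about 82%. At 25% vs 15% it is only about 24% even with grouping. Overlap, uneven spread and SOC pooling narrow the gain further.

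No planned result becomes wrong and no data are lost. The documents do not support the stronger conclusion that the planned tables cannot reveal a tolerability difference. This is a cheap improvement, not a defect that threatens the trial.

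**What to change.** Add to Section 23.b, before unblinding:

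- A fixed list of preferred terms forming 'any local anorectal reaction', built from the reactions named in Sections 14 and 22.a.
- The number and percentage of subjects with at least one such event per arm, with the risk difference and its 95% interval, labelled as a descriptive estimate. The SOC/PT tables stay as they are.
- A rule for itching and burning that represent worsening of the treated condition under Section 24, for example showing the row with and without those terms.

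The cost is one definition and one table row (two if shown both ways), from data already collected. The term list must be agreed at the blinded coding review. One limit remains: itching or burning recorded only as efficacy data will not be counted, and the table footnote should say so.
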